#### 16.5 **Regulatory Documentation and Records Retention**

The Investigator is accountable for the integrity, retention, and security of all study related data. The Investigator must maintain accurate, complete, and current records relating to the clinical study. The Investigator must maintain the required records during the investigation and for a period of time specified by local law or per the Clinical Study Agreement, whichever is longer. If the Investigator retires, relocates, of for any other reason withdraws from responsibility of keeping the study records, the Sponsor must be notified and suitable arrangements made for retention of study records and source documents needed to comply with national and international regulations.

Alcon - Business Use Only Statistical Analysis Plan

Effective Date: 19-Dec-2016

Document: TDOC-0052724

Version: 1.0; CURRENT; Most-Recent; Effective

Status: Effective

Short Title:

**Statistical Analysis Plan
RFL605-P001 / NCT02987660**

Full Title:

**Statistical Analysis Plan
RFL605-P001**

Protocol Title: Comparison of Topography Guided LASIK with WaveLight EX500 to SMILE with Zeiss VisuMax

Project Number: A02827

Protocol TDOC Number: TDOC-0052425

Author:

[REDACTED]

[REDACTED]

Template Version: Version 4.0, approved 16MAR2015

Approvals: See last page for electronic approvals.

Job Notes:

This is the original (Version 1.0) Statistical Analysis Plan for this study. This version of the Statistical Analysis Plan is based on Version 1.0 of the study protocol.

[figure not shown]
[figure not shown]
[figure not shown]
Executive Summary:

Key Objectives:

The primary objective of the study is to demonstrate that Topography Guided Laser in situ keratomileusis (LASIK) is superior to Small incision lenticule extraction (SMILE) in the percentage of eyes with manifest refraction cylinder ≤ 0.5 D at 3 months.

Decision Criteria for Study Success:

The primary objective will be considered met if the percentage of eyes with manifest refraction cylinder within (\leq) 0.5 D in the Topography Guided LASIK arm is statistically significantly different from the SMILE arm at 3 months (Month 3) in favor of the Topography Guided LASIK arm.

| | | |
|--|--|----|
|  | | 16 |
|  | | 17 |
|  | | 17 |
|  | | 17 |
| 5.4 | Multiplicity Strategy..... | 18 |
| 5.5 | Handling of Missing Data | 19 |
| 6 | Safety Analysis Strategy | 19 |
| 6.1 | Safety Endpoints..... | 19 |
| 6.2 | Safety Hypotheses | 20 |
| 6.3 | Statistical Methods for Safety Analyses..... | 20 |
| 6.3.1 | Adverse Events | 20 |
| 6.3.2 | Best Corrected Visual Acuity | 21 |
| 6.3.3 | Biomicroscopy Findings/Slit Lamp Examination | 22 |
| 6.3.4 | Intraocular Pressure | 22 |
| 6.3.5 | Dilated Fundus Examination | 22 |
| 6.3.6 | Mesopic Uncorrected Contrast Sensitivity | 22 |
| 6.3.7 | Subject Reported Outcomes | 23 |
| 6.3.8 | Surgical Problems..... | 23 |
| 6.3.9 | Nomogram..... | 23 |
| 6.3.10 | Surgical report | 23 |
| 6.3.11 | Device Deficiencies..... | 24 |
| 7 | Sample Size and Power Calculations | 24 |
| 8 | References..... | 24 |
| 9 | Revision History | 25 |
| 10 | Appendix..... | 25 |
| 10.1 | Imputation rules | 25 |
| 10.1.1 | AE Date Imputation..... | 25 |
| 10.1.1.1 | AE End Date | 25 |
| 10.1.1.2 | AE Start Date..... | 25 |

List of Figures

| | | |
|------------|-------------------|---|
| Figure 1-1 | Study design..... | 8 |
|------------|-------------------|---|

List of Abbreviations

| | |
|--------|--|
| A | Axis |
| ADE | Adverse device effect |
| AE | Adverse event |
| ATC | Anatomical therapeutic classification |
| BCVA | Best corrective visual acuity |
| C | Cylinder |
| CI | Confidence interval |
| CSR | Clinical study report |
| DBL | Database lock |
| eCRF | Electronic case report form |
| ICF | Informed consent form |
| IOP | Intraocular pressure |
| ITT | Intent-to-Treat |
| LASIK | Laser in situ keratomileusis |
| MedDRA | Medical Dictionary for Regulatory Activities |
| MRSE | Manifest refraction spherical equivalent |
| OD | Right eye |
| OS | Left eye |
| OU | Both eyes |
| RSVP | Refractive Status and Vision Profile |
| SAP | Statistical analysis plan |
| SADE | Serious adverse device effect |
| SAE | Serious adverse event |
| SD | Standard deviation |
| SE | Standard error |
| SMILE | Small incision lenticule extraction |
| SQDES | Short questionnaire for dry eye syndrome |
| SOC | System organ class |
| TEAE | Treatment-emergent AE |
| UCVA | Uncorrected visual acuity |
| WHO | World Health Organization |

1 Study Objectives and Design

This statistical analysis plan (SAP) describes the statistical analysis outlined in Section 15 of the study protocol (Clinical Trial Protocol Version 1.0) along with any additional analyses, specifications or deviations from the protocol planned before database lock (DBL).

[figure not shown]
1.1 Study Objectives

The primary objective of the study is:

- To demonstrate that Topography Guided Laser in situ keratomileusis (LASIK) is superior to Small incision lenticule extraction (SMILE) in the percentage of eyes with manifest refraction cylinder ≤ 0.5 D at 3 months.

The secondary objectives are:

- To demonstrate that Topography Guided LASIK is superior to SMILE in mean manifest refraction cylinder at 3 months.
- To demonstrate that Topography Guided LASIK is superior to SMILE in mean uncorrected visual acuity (UCVA) at 3 months.

The safety objectives are:

- To evaluate the adverse events (AEs) associated with Topography Guided LASIK and SMILE.
- To evaluate post-surgery BCVA after Topography Guided LASIK and SMILE.
- To evaluate mesopic uncorrected contrast sensitivity after Topography Guided LASIK and SMILE.

- To evaluate quality of vision and vision related quality of life after Topography Guided LASIK and SMILE.

[figure not shown]
1.2 Study Description

This is a prospective, parallel group, multi-center, randomized, observer masked study. The study will enroll subjects requiring refractive correction of myopia and astigmatism who meet the protocol inclusion and exclusion criteria. The expected duration of subject participation in the study is up to 15 months with 7 planned study visits (including Pre-surgery Visit).

The study involves a Pre-Surgery Visit (ranging from 1 to 45 days prior to the Surgery Visit) followed by a 12-month post-surgery period (see Figure 1-1). The visits are as follows:

- Pre-Surgery/ Screening Visit (Day -45 to Day -1)
- Surgery (Day 0)
- Day 1 (Day 1)
- Week 1 (Day 7 \pm 2)
- Month 1 (Day 28 \pm 7)
- Month 3 (Day 84 \pm 14)
- Month 12 (Day 330 to Day 375)

Figure 1-1 Study design

1.3 Randomization

The randomization scheme will be generated and maintained by the Sponsor's (or designee) unmasked personnel who are not involved in the conduct or analysis of the study. Randomization will be implemented using Medidata Balance[®].

The randomization will be stratified by study site to ensure a balance of surgery allocations within each investigational site. Randomization will be in a 1:1 ratio.

1.4 Masking

This is an observer masked study. This means that site personnel performing the manifest refraction subjective assessment and all UCVA testing after randomization will remain masked with regard to treatment assignment until after the final DBL.

Surgery assignment may be known to Alcon, Novartis, and other site personnel (e.g., nurses and technicians involved with the surgery, staff entering data in the electronic case report form (eCRF), site personnel administering other study related procedures, e.g. Refractive Status and Vision Profile [RSVP] and Short questionnaire for dry eye syndrome [SQDES] questionnaires). However they will not reveal the surgery assignment to masked site personnel at any time during the study.

1.5 Interim Analysis

There is no formal interim analysis planned for this study. However, the main analysis will occur after the last subject completes the 3 months post-surgery follow-up (Day 84 ± 14). Subjects will then be followed up for an additional 9 months post-surgery (i.e. in total 12 months [Day 330 to Day 375] after surgery) for safety [REDACTED] parameters.

2 Data Analysis General Information

All analyses will be performed using SAS[®] statistical software (Version 9.4 or a more recent version), unless otherwise noted.

Assessments documented in the database that occur as “bilateral” (i.e. both eyes [OU]) will be summarized and listed for each eye separately. To facilitate derivations and analysis based on the eye, database records for bilateral will be split into two records containing identical information as the original record with the exception of the laterality which shall be recoded to “Right” (i.e. right eye [OD]) and “Left” (i.e. left eye [OS]), respectively. It should be noted that dependent on the assessment and at the discretion of the medical team, the assessment may only be counted once.

Data will be summarized with respect to background and demographic characteristics, primary, secondary, [REDACTED] along with safety observations.

Descriptive statistics (the number of non-missing observations, mean, median, standard deviation [SD], minimum, and maximum values) will be presented for continuous variables. The following number of decimal places will be used: mean values to 1 more decimal place than the raw data; median, minimum, and maximum to the same number of decimal places as the raw data and SD to 2 more decimal places than the raw data.

For categorical variables for background and demographic characteristics, the number and percentage of subjects/ eyes for each category within a variable will be calculated for non-missing data. If a count of zero is obtained for categorical data, the zero count and percentage will still be displayed. A row (category) denoted “Missing” will be included in count tabulations if a non-zero count of missing values is present for either of the surgery groups. In addition, the corresponding percentage for this row will be displayed.

Change from baseline (pre-surgery) (where relevant) will only be summarized for subjects with both baseline (pre-surgery) and post-surgery data for the relevant visit.

Unless otherwise specified, all statistical tests will be two-sided, performed using a 5% significance level and 95% (two-sided) confidence intervals (CIs) will be presented.

All data will be listed by subject and eye (if applicable), unless stated otherwise.

2.1 General Definitions

All analyses will be based on assessments according to the investigator, with the exception of the subject reported outcomes (RSVP questionnaire, SQDES). This study will consist of the following epochs:

- a screening period
- a post-surgery period

Surgery/ treatment refers to:

- Topography Guided LASIK
- SMILE

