## Intensity (Severity)

Mild An AE is mild if the subject is aware of but can easily tolerate the sign or

symptom.

Moderate An AE is moderate if the sign or symptom results in discomfort significant

enough to cause interference with the subject's usual activities.

Severe An AE is severe if the sign or symptom is incapacitating and results in the

subject's inability to work or engage in their usual activities.

For every AE in the study, the Investigator must assess the causality (Related or Not Related to the medical device or study procedure). An assessment of causality will also be performed by Study Sponsor utilizing the same definitions, as shown below:

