## Causality

Related An AE classified as related may be either definitely related or possibly related

where a direct cause and effect relationship with the medical device or study procedure has not been demonstrated, but there is a reasonable possibility that

the AE was caused by the medical device or study procedure.

Not Related An AE classified as not related may either be definitely unrelated or simply

unlikely to be related (i.e, there are other more likely causes for the AE).

The Study Sponsor will assess the AEs and may upgrade the Investigator's assessment of seriousness and/ or causality. The Study Sponsor will notify the Investigator of any AE that is upgraded from non-serious to serious or from unrelated to related.

Alcon - Business Use Only Protocol - Clinical Effective Date: 19-Mar-2017 Page 66 of 81

Document: TDOC-0052425 Version: 2.0; Most-Recent; Effective; CURRENT

Status: Effective

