6.3.1 Adverse Events

The applicable definition of an AE is in the study protocol. All AEs occurring from when a subject signs the ICF to when a subject exits the study will be accounted for in the reporting. Analysis and presentation of AEs occurring during the 45 day pre-surgery period (the screening period) will be separated from those occurring during the post-surgery period where a comparative evaluation (descriptive only) of treatment-emergent AEs (TEAEs) is intended. A TEAE is an event not present prior to surgery (Topography Guided LASIK, SMILE) or any pre-existing event that worsens following surgery. The period for TEAE analysis starts from when study treatment has begun to 12 months post-surgery (Day 330 to Day 375). Study treatment will be considered to have begun once the flap creation is initiated for Topography Guided LASIK and once the laser touches the eye for SMILE.

Descriptive summaries (subject counts and percentages, event counts) by surgery group for specific AEs will be presented by primary SOC and PT of the Medical Dictionary for Regulatory Activities (MedDRA) dictionary (Version 19.0 or a more recent version). The SOCs will be presented in alphabetical order. PTs will be ordered for each surgery group in decreasing proportion in the Topography Guided LASIK surgery group of interest (study surgery group 1). The following summary tables will be provided:

- Ocular AEs for all eyes in the Safety Analysis Set (TEAE only)
- Ocular SAEs for all eyes in the Safety Analysis Set (TEAE only)
- Adverse device effects (ADEs) for all eyes in the Safety Analysis Set (TEAE only)

- Serious ADEs (SADEs) for all eyes in the Safety Analysis Set (TEAE only)

Both subject and event counts will be presented for AEs. Subject counts refer to the number of subjects with the respective AE of interest. Subjects who experience multiple AEs for a PT will be counted once, similarly for subjects with multiple AEs per SOC, for subject counts. Event counts refer to the number of occurrences of the respective AE of interest, regardless of whether a subject already had this event.

Individual subject's listings will also be provided. These will include:

- Ocular AEs for all eyes in the Safety Analysis Set
- Ocular AEs for all eyes not in the Safety Analysis Set
- Non-ocular AEs for all enrolled subjects
- Listing of deaths for all enrolled subjects

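### SAP 2.1 makes no exception for sponsor upgrades of seriousness or causality, so on a literal reading the ocular SAE, ADE and SADE tables could omit upgraded events

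*SAP*

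**What the plan says.** SAP 2.1 (General Definitions) says whose judgement the analyses use: "All analyses will be based on assessments according to the investigator, with the exception of the subject reported outcomes (RSVP questionnaire, SQDES"). The two questionnaires are the only exception.

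Protocol 13.3 provides for a second judgement on the same event. On causality: "An assessment of causality will also be performed by Study Sponsor utilizing the same definitions, as shown below". On seriousness as well as causality: "The Study Sponsor will assess the AEs and may upgrade the Investigator's assessment of seriousness and/ or causality". The consequence it states is a notice to the site: "The Study Sponsor will notify the Investigator of any AE that is upgraded from non-serious to serious or from unrelated to related".

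SAP 6.3.1 plans four summary tables. One counts all ocular treatment-emergent events. The other three depend on the attributes that can be upgraded. Seriousness decides who enters the table headed "Ocular SAEs for all eyes in the Safety Analysis Set (TEAE only"). Relatedness decides the ADE table, and both attributes together decide the SADE table; these two are restricted to the same eyes and to treatment-emergent events.

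None of the three names an assessor, and neither do the definitions of ADE, SAE and SADE in the protocol glossary (Section 4).

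**The concern.** The protocol foresees that one event may carry two classifications, while the SAP's only rule on the matter points to one of them. A sponsor upgrade exists to correct an event that the site rated too low. If the tables are filled from the investigator's value alone, that correction need not reach the reported comparison, and the SAE, ADE and SADE counts could be lower than those the sponsor itself recognises.

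This matters more here because safety is purely descriptive. Protocol 15.7 and SAP 6.2 plan no tests, so these counts are themselves the reported safety comparison. Evaluating adverse events is also the first safety objective. In addition, SAP 1.4 says the sponsor may know the assignment. If the governing classification is not fixed in advance, it could be chosen once the upgrades in each arm are known.

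**Working it through.** The plan gives no figure to reproduce on this point, so the check sets the texts side by side.

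**Step 1: which rule picks the assessor?** SAP 6.3.1 and the protocol glossary are silent. SAP 2.1 is the only text that speaks to it, and it names the investigator without excepting sponsor upgrades.

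**Step 2: what happens to the record after an upgrade?** Protocol 13.3 states only that the investigator is notified. Three other provisions could lead to a revised eCRF:
- Protocol 13.3: further relevant information after the initial report goes into the eCRF.
- Protocol 13.6: the site should pass on changes to events already reported.
- Protocol 14.2: the sponsor may query entries and expects the site to make corrections.

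None of them mentions upgrades, and none obliges the investigator to change a judgement. Whether the recorded value changes is therefore open.

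**Step 3: which tables are affected if the recorded value is not revised?** Let S = serious and R = related, each 0 or 1. An ocular treatment-emergent event enters the AE table always, the SAE table if S = 1, the ADE table if R = 1, and the SADE table if S = 1 and R = 1. Every possible upgrade:

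| Investigator (S, R) | After upgrade (S, R) | Missing from | Still in |
|---|---|---|---|
| 0, 0 | 1, 0 | SAE | AE |
| 0, 0 | 0, 1 | ADE | AE |
| 0, 0 | 1, 1 | SAE, ADE, SADE | AE |
| 0, 1 | 1, 1 | SAE, SADE | AE, ADE |
| 1, 0 | 1, 1 | ADE, SADE | AE, SAE |

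Three of the four tables can be affected, and only a double upgrade affects all three. The overall ocular AE table never loses an event. Non-ocular SAEs appear only in listings under SAP 6.3.1, whoever assesses them.

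**Step 4: size.** Protocol 15.9 and SAP 7 expect 200 treated subjects per arm. One upgraded subject not already counted on a given table line changes that line's subject percentage by 1/200 = 0.5 points. This is the size of one step, not an estimate of the effect. The number of steps depends on how many events are upgraded and not revised by the site, and the documents give neither figure.

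**The case against.** A reader might infer that the SAP excludes upgraded events from the safety tables, or from the report. The documents do not say that. The sentence in SAP 2.1 is general, and the only contrast it draws is between the investigator's assessments and subject-reported data. Protocol 13.3 speaks of upgrading the investigator's own assessment, which is compatible with the recorded value being changed. The query process could also lead a site to revise its entry. All of this stands, and it is why the point is conditional. It does not close the gap: no text says that an upgrade replaces the recorded value or which value is analysed when the two differ.

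A reader might also infer that mandatory SAEs missed by a site would go uncorrected. That is too strong. Protocol 13.1 requires certain ocular events to be reported as serious, so a missed one is a reporting error that a query can correct. A loss of two or more lines of BCVA also has its own listing in SAP 6.3.2, built from measured acuity.

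A reader might further express the effect as a large share of an arm's SAEs. That needs both an SAE rate and an upgrade rate, and the documents give neither.

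Finally, investigator-based tables are defensible, because the sponsor may know the assignment and the test laser is its own product. This also stands. It argues for showing both classifications, not for leaving the choice unstated.

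**Conclusion.** The point holds as a conditional gap. SAP 2.1 makes the investigator's assessment govern all analyses and does not provide for the upgrades that Protocol 13.3 allows. On a literal reading, an upgraded ocular treatment-emergent event would be missing from one, two or all three of the SAE, ADE and SADE tables, depending on which attribute was upgraded. It would remain in the overall ocular AE table and in the listings, so no event disappears from the report.

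The conclusion rests on two conditions: that SAP 2.1 is applied as written to seriousness and causality, and that the site does not revise the eCRF after notification. The documents settle neither. The size is unknown and may be zero. The effectiveness analyses do not depend on AE classification and are not touched. This is a cheap improvement to the plan, not a flaw that undermines the safety evaluation.

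**What to change.** Add to SAP 2.1 an exception for the seriousness and causality of adverse events. State in SAP 6.3.1 that an event counts as serious if either the investigator or the sponsor so classes it, and as related on the same basis, with one rule for both arms. Show both classifications in the AE listings and report the number of upgrades by arm, so that the investigator-only counts can be recovered.

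The cost is a sentence or two in the SAP, one flag in the AE dataset and one small summary. The current SAP was written for Version 1.0 of the protocol, which is now at Version 2.0, and Protocol 15 requires the SAP to be final only before database lock, so the change can go into an update.

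The downsides are that SAE and ADE counts may rise slightly, and that the upgrades come from a party that may know the assignment. The second is the reason for showing both classifications rather than only the combined one.

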2.2 Definition of Baseline Date

Baseline date is referred to as Surgery (Day 0) of the study. It is defined as the date of surgery, for treated subjects/ eyes.

2.3 Baseline and Post-baseline Definitions

The baseline (pre-surgery) value for effectiveness and safety variables is the last available, non-missing, scheduled or unscheduled value collected prior to surgery.

All data collected after Surgery (Day 0) are defined as post-baseline.

2.4 Unscheduled Visits

All data collected at unscheduled visits will be listed.

AEs, slit lamp examination findings and dilated fundus findings collected at unscheduled visits will be reported.

3 Analysis Sets

Assignment of study eyes to the appropriate analysis set(s) will be determined prior to DBL. For the purposes of this study, the treatment will be considered to have begun once the flap

creation is initiated for Topography Guided LASIK and once the laser touches the eye for SMILE.

The **Intent to treat (ITT) Analysis Set** will contain all study eyes for which study treatment has begun for the set of subjects that are randomized; all eyes will be assigned to the treatment to which they are randomized.

The **Safety Analysis Set** will contain all study eyes for which study treatment has begun; all eyes in the Safety Analysis Set will be assigned to the treatment actually received.

All subjects who satisfy the inclusion and exclusion criteria, and who sign the informed consent form (ICF), will be considered enrolled in the study.

The ITT Analysis Set will be used to display subject disposition, background and demographic characteristics, medical history, and the analysis of the effectiveness endpoints. The Safety Analysis Set will be used for the analysis of the safety endpoints.

It should be noted for subject-level (group-level) data, the analysis will be based on the subject-level version of the respective analysis set (i.e. the subject must have at least one eye for which treatment has begun).

4 Subject Characteristics and Study Conduct Summaries

Subject characteristics and study conduct summaries include tables and listings such as a subject disposition table, background and demographic characteristics tables (including age, sex, race, and ethnicity), listing of study surgery assignment by investigator, and listing of subjects excluded from the analysis sets. Descriptive summary statistics will be presented by surgery group and overall for the ITT Analysis Set, unless otherwise specified.

No inferential tests for differences in subject characteristics between surgery groups will be performed.

